1.1 Study Background

Post-Percutaneous Coronary Intervention (PCI) Fractional Flow Reserve (FFR) values ≥ 0.90 are associated with better clinical outcomes for patients but the available data suggest that, despite angiographically satisfactory results, this target is actually achieved in less than 40% of cases.

Using post-PCI FFR to guide further stent optimisation and/or additional stenting in the target vessel can increase the frequency with which optimal post-PCI FFR results are achieved. However, there are additional costs associated with the routine use of post-PCI FFR and it is not clear how often it is even possible to increase the initial post-PCI FFR result to ≥ 0.90 . This uncertainty makes it currently difficult to either recommend the routine use of post-PCI FFR or justify its cost.

The Target FFR Study is a prospective, randomised controlled trial assessing the efficacy of an FFR-guided optimisation strategy in achieving optimal post-PCI FFR results in a series of consecutive patients undergoing standard PCI for stable angina and non-ST-segment elevation myocardial infarction (NSTEMI).

The study will also provide randomised, 'real-world' data on the incidence of suboptimal post-PCI FFR results and systematically elucidate the responsible mechanisms where these occur. The data from this developmental study could support a subsequent definitive phase 3 study of the impact of FFR-targeted PCI on clinical outcomes.

1.2 Study Objectives

Research Hypotheses:

The null hypothesis is that there is no difference in the proportion of patients with final post-PCI Fractional Flow Reserve (FFR) results ≥ 0.90 between those receiving a coronary physiology-guided optimisation strategy and those receiving standard care. The alternative hypothesis is that there is a difference between the two treatment approaches.

Primary Objective:

To determine the feasibility and efficacy of using a coronary physiology-guided optimisation strategy to achieve a final post-percutaneous intervention (PCI) Fractional Flow Reserve (FFR) result ≥ 0.90 compared to standard care.

Secondary Objectives:

Further assessment using several alternative methods of measuring the efficacy of using a coronary physiology-guided optimisation strategy as defined below.

1.3 Study Design

A single centre, parallel group, randomised controlled clinical trial. Patients are randomised in a 1:1 ratio to receive either a physiology-guided optimisation strategy (potentially undergoing additional stent post-dilation and/or further stenting in the target vessel as appropriate) or standard care. The framework for the trial is testing the superiority of the extra treatment in terms of its efficacy.

1.4 Randomisation

Randomisation will be performed using a 1:1 variable block (2,4,6) randomisation method generated from within the study's electronic Case Report Form (eCRF) platform, Castor EDC.

1.5 Blinding

Patients will not be informed of their final coronary physiology results. FFR results will not be displayed on the procedure-room monitor and the physiology interface will only be visible to research staff in the control room. These results will only be disclosed to the operator for patients with initial post-PCI FFR <0.90 who are randomized to receive the optimisation strategy. The rationale for maintaining operator-blinding for all other post-PCI physiology results is to try and minimise the potential Hawthorne effect ('observer effect') the study could have on local PCI practices.

1.6 Sample Size and Power

260 patients will be randomised.

Previous studies suggest that approximately 40% of patients in the control arm will have a post-PCI FFR ≥ 0.90 .(1-5)

This is in keeping with pilot data from our own institution where, among 50 patients who underwent post-PCI FFR assessment, an initial result ≥ 0.90 was achieved in only 16 /50 (32%).

It is hypothesised that the proposed PIOS intervention will increase the proportion of patients with a final post-PCI FFR ≥ 0.90 by approximately 20% compared to the control group. (a relative improvement of at least 50%).

A sample size of 130 patients per group would be required to have 90% power to detect a 20% absolute difference between groups at the 5% significance level.

1.7 Study Population

Consecutive patients with stable angina or Non-ST segment Elevation Myocardial Infarction (NSTEMI) referred to the cardiac catheterisation lab for invasive management who have been selected to undergo PCI based on either angiographic appearances or prior FFR assessment.

1.7.1 Inclusion Criteria

- Patients >18 years of age with coronary artery disease including stable angina and NSTEMI.
- Participants must be able to provide informed consent.

1.7.2 Exclusion Criteria

- PCI in a coronary artery bypass graft
- PCI to an in-stent restenosis (ISR) lesion
- PCI to a target artery providing Rentrop grade 2 or 3 collateral blood supply to another vessel
- Inability to receive adenosine (for example, severe reactive airway disease, marked hypotension, or advanced atrioventricular block without pacemaker).
- Recent (within 1 week prior to cardiac catheterization) ST-segment Elevation Myocardial Infarction (STEMI) in any arterial distribution (not specifically target lesion).
- Severe cardiomyopathy (ejection fraction <30%).
- Renal insufficiency such that an additional 20 to 30 mL of contrast would, in the opinion of the operator, pose unwarranted risk to the patient.

1.8 Statistical Analysis Plan (SAP)

1.8.1 SAP Objectives

The objective of the SAP is to describe the statistical analyses to be carried out for the Target FFR Study.

1.8.2 General Principles

All relevant study data will be summarised for the randomised population overall, and by randomised group.

The number of observations and number of missing values will be reported; continuous variables will be summarised using the mean, standard deviation (SD), median, quartiles and range; categorical variables will be summarised with frequencies and percentages.

Where relevant, changes from baseline will be summarised.

Efficacy analyses will be carried out according to the intention to treat principle, that is, in relation to randomised treatment allocation, rather than treatment received. Safety analyses will be carried out in relation to treatment received.

1.8.3 Current Protocol

The current protocol at the time of writing is version 1.0, dated 08 June 2017. Future amendments to the protocol will be reviewed for their impact on this SAP, which will be updated only if necessary

1.8.4 Deviations to Those Specified in Study Protocol

No deviations to the analyses specified in the study protocol are planned.

1.8.5 Additional Analyses to Those Specified in Study Protocol

Additional pre-specified analyses to the study protocol are outlined below in 2.7

1.8.6 Software

Analyses will be carried out using SPSS Statistics, version 25 and R, version 3.4 or above.

2. Analysis

All applicable analyses will be 2-sided and will be performed using a 5% significance level. All confidence intervals presented will be 95% and two-sided.

2.1 Study Populations

The screened population will consist of all patients screened for inclusion in the study as recorded in the study screening logs.

The Full Analysis Set (FAS) will consist of all patients who were randomised. Analyses within the FAS will compare treatment groups as randomised, regardless of which (if any) treatment was received.

The Safety Set (SS) will consist of all patients who were randomised and received treatment. Analyses within the SS will compare treatment groups according to the treatment received.

The numbers of patients included in the SP and FAS will be reported as a whole and by age and by sex. Reasons for exclusion from the FAS will be summarised as a whole, by age and by sex.

The numbers of patients included in the FAS and SS will be reported as a whole and by treatment group. The numbers of patients in the FAS who did not receive treatment or received a different treatment to that allocated at randomisation, will be reported.

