- Recent (within 1 week prior to cardiac catheterization) ST-segment elevation myocardial infarction (STEMI) in any arterial distribution (not specifically target lesion).
- Severe cardiomyopathy (ejection fraction <30%).
- Renal insufficiency such that an additional 20 to 30 mL of contrast would, in the opinion of the operator, pose unwarranted risk to the patient.

Methods/Design:

Informed consent will be obtained prior to cardiac catheterisation in all potential subjects conforming to the inclusion and exclusion criteria.

Patients will then be randomised to one of two groups (described below) and PCI will be performed, using a pressure guidewire, according to standard practice at the Golden Jubilee National Hospital (including lesion pre-dilation and post-dilation of the stented segment).

Group 1 (PIOS Group):

Operator-blinded FFR will be measured post PCI.

If FFR is ≥ 0.90 , no further intervention will be performed and the procedure is considered complete.

If FFR is < 0.90 , the result will be disclosed to the operator and a hyperaemic pressure wire pullback during either a standard peripheral intravenous adenosine infusion (140mcg/kg/min) or an intracoronary adenosine infusion (360mcg/min) via a microcatheter will be performed. Depending on the result the operator would then have the following options:

- A. If there is a step-up of ≥ 0.05 across the stented segment(s) further post-dilatation with a 0.25 - 0.50mm larger non-compliant balloon to at least 18 atmospheres should be performed followed by repeat FFR. Alternatively, the operator may choose to employ intracoronary imaging (IVUS or OCT) to guide post-dilation/optimisation of the stented segment.

- B. If there is a step-up of ≥ 0.05 across a relatively focal (<20mm) unstented segment which is technically suitable for further stenting then a further stent should be implanted followed by repeat FFR.
- C. If the FFR remains < 0.90 after steps A +/- B, a further FFR pullback will be performed. If the criteria for Step B are again met, one additional stent may be deployed and a final FFR pullback performed. Following this, the FFR result will be accepted.
- D. If the residual pressure gradient is interpreted to reflect diffuse atherosclerosis with no focal step-ups, the result is accepted.

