2.2 Baseline Characteristics

Baseline characteristics will be summarised in the FAS as a whole and by treatment group. The following baseline characteristics will be reported:

- Demographics: age (years), sex (male, female), height, weight, BMI, ethnicity (White or White British, Asian or Asian British: South Asian, Asian or Asian British: Chinese, Asian or Asian British: Other Asian, Black or Black British, Mixed or Multiple, Other)
- Lifestyle Factors: Smoking Status (No, Current, Ex-Smoker <12 months, Ex-Smoker >12 months)
- Vital Sign Observations: heart rate, blood pressure
- Pharmaceutical therapy (medications used for treatment of cardiovascular disorders including primary and secondary therapies)
 - Number of antianginal medications
- Medical History including Risk Factors (yes/no unless otherwise stated)
 - Indication for Angiogram (Stable Angina, ACS-NSTEMI, ACS-Unstable Angina)
 - Time since NSTEMI
 - Troponin Assay Used and Peak Troponin Recorded if NSTEMI
 - Hypertension
 - Hypercholesterolaemia
 - Diabetes
 - TIA/Stroke
 - CKD
 - Thyroid Dysfunction
 - Pacemaker
 - ICD
 - Atrial Fibrillation
 - Heart Failure (No, HF-rEF, HF-pEF)
 - NYHA Class if Heart Failure (1-4)
 - Previous PCI
 - Previous MI
 - History of Previous MI in Target Vessel if Yes
 - CABG
 - Angina
 - Canadian Cardiovascular Society (CCS) Class if Angina (1-4)
 - Valvular Heart Disease
 - Valve Replacement/Repair
 - Family History of CAD
- Health Status questionnaire scores:
 - Seattle Angina Questionnaire
 - EQ-5D-5L
- Procedural Characteristics
 - Vascular Access (Radial, Femoral, Brachial)
 - Sheath Size

- Multivessel Procedure (Yes, No)
- Procedure Time
- Duration of Research Protocol
- Contrast Dose
- Dose Area Product
- Radiation Dose
- Total Duration of Adenosine Infusion
- Total Dose of Adenosine
- Total Number of Stents Deployed in Study Artery
- Total Length of Stents Used in Study Artery
- Diameter of Largest Balloon used for PCI
- Largest Stent Diameter

- Angiographic Characteristics
 - Target Coronary Artery Segment
 - Lesion Severity by Operator's Visual Assessment (Normal, Plaque Disease, <25%, 25-49%, 50-74%, 75-94%, >/= 95%, Subtotal Occlusion, Occluded)
 - AHA Lesion Type
 - Lesion APPROACH Score
 - Gensini Score
 - QCA Lesion Length
 - Pre- and Post-PCI QCA Diameter Stenosis
 - Pre- and Post-PCI QCA Area Stenosis
- Pre- and Post-PCI Coronary Physiology Test Results
 - Ratio of distal coronary to aortic pressure (Pd/Pa)
 - Diastolic Pressure Ratio (dPR)

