2.5.2 Adverse Outcomes During Coronary Function Tests

Information on adverse events related to the additional coronary function tests will be collected prospectively.

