2.5.3 Serious Adverse Events

The characteristics of serious adverse events (SAEs) that occur on or before the date of the 3-month follow-up will be summarised as for the SS as a whole and

by randomisation group. SAEs will be summarised with respect to severity, relationship to study procedures, outcome and duration.

Separate summaries will be provided for fatal SAEs.

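### Limiting the Safety Set to treated patients leaves SAEs that stop a case during the pre-PCI study tests out of the SAE summary: a minor, partial gap

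*SAP*

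**What the plan says.** SAP 2.1 defines the set: "The Safety Set (SS) will consist of all patients who were randomised and received treatment". It does not say what counts as treatment. The same section provides for randomised patients outside the set, but only as a count: "The numbers of patients in the FAS who did not receive treatment" are to be reported.

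SAP 2.5.3 ties the SAE summary to this set. SAEs occurring "on or before the date of the 3-month follow-up will be summarised as for the SS as a whole and" by randomised group, and they are to be described by severity, link to study procedures, outcome and duration. It then adds: "Separate summaries will be provided for fatal SAEs". No other set is named for the fatal events.

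SAP 2.5.2 covers the tests themselves: "Information on adverse events related to the additional coronary function tests will be collected prospectively". It names no analysis set and no tabulation.

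Two further places show how exposure can come before treatment. SAP 2.2 lists "Pre- and Post-PCI Coronary Physiology Test Results", and SAP 2.3.2 has many outcomes defined as change from the pre-PCI value, so invasive physiology is measured before PCI. Protocol Methods/Design puts randomisation after consent and before PCI: "Patients will then be randomised to one of two groups (described below) and PCI will be performed, using a pressure guidewire".

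**The concern.** A safety population should be defined by exposure to whatever could cause the harm being counted. Here the harm of interest includes harm from the research measurements, because 2.5.3 sets out to classify SAEs by their link to study procedures. Membership, however, depends on having gone on to treatment. A serious event during the pre-PCI tests that ends the case would itself take the patient out of the set. The exclusion therefore depends on the outcome: the events most likely to be dropped are those severe enough to stop the procedure.

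What is at stake is the completeness of the SAE table and, because of where it sits, the fatal-SAE summary. SAE counts in a trial of this size may be low, so one or two omitted events could be visible in the reported percentage.

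**Working it through.** The point is about who falls in which set, so I traced one patient through the text and then sized the gap.

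**1. Are the tests part of treatment?** SAP 1.3 describes what patients are randomised to: the physiology-guided optimisation strategy or standard care. SAP 2.4 lists completion of the diagnostic protocol as a feasibility outcome, and 2.5.2 calls the coronary function tests additional. The SAP's own vocabulary therefore separates the tests from the treatment, though it never says so outright.

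**2. Trace a patient whose case stops during the pre-PCI tests.**

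| Order of events | FAS | Safety Set | SAE summary (2.5.3) |
|---|---|---|---|
| Randomised, tests started, stopped before PCI | in | out (not treated) | missing |
| Tests started, stopped before randomisation | out | out (not randomised) | missing |

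The documents do not say which order applies. The event is missing from 2.5.3 in both, for different reasons.

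**3. What is still reported elsewhere?** For randomised patients, SAP 2.3.2 includes cardiac death and MI (within target vessel failure) and procedural complications. These sit under Efficacy Outcomes, which SAP 1.8.2 analyses by intention to treat. What stays outside is (a) other SAEs, such as an arrhythmia or an adenosine reaction, or a non-cardiac death, and (b) for every such patient, the 2.5.3 classification by severity and link to study procedures. In the second row of the table, 2.3.2 does not help either, because the patient was never randomised.

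**4. Size.** The plan gives no figure for such events. Its only relevant number is 260 randomised (130 per group). That sample size reproduces: for 40% versus 60%, two-sided 5%, 90% power and pooled variance, n = [1.960 × √(2 × 0.5 × 0.5) + 1.282 × √(0.24 + 0.24)]² / 0.20² = 129.3, so 130 per group. It serves here only as the denominator.

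Let r be the proportion of patients with an SAE that stops the case during the pre-PCI tests. This is an assumption, not a figure from the documents. The expected number omitted is 260 × r, and the chance of at least one omission is 1 − (1 − r)^260.

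| Assumed r | Expected number omitted | Chance of at least one |
|---|---|---|
| 0.2% | 0.5 | 41% |
| 0.5% | 1.3 | 73% |
| 1% | 2.6 | 93% |
| 2% | 5.2 | 99% |

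Each omitted patient is 1/260 = 0.4% of those randomised; two are 0.8% and three are 1.2%.

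**The case against.** The strongest reply is that the loss is not established. Randomised and treated is a conventional safety-set definition. The protocol has PCI performed with the pressure wire, so a wire injury after randomisation could fairly be read as happening during the allocated procedure. The arms are strategies rather than completed stents, and on that reading the patient was treated and stays in. This has some force, since the term is undefined. But SAP 1.3, 2.4 and 2.5.2 point to the narrower reading, and if the wider one is intended, the SAP needs to say so.

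The second reply is that the order of randomisation and pre-PCI tests is not given. That is correct. It does not remove the gap, but a fix limited to randomised patients might not close it.

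The third is that much of the harm is counted elsewhere. This stands in large part, as step 3 of the working shows. A reader might infer that serious harm from the tests disappears from the trial's results altogether; the documents do not support that.

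The fourth is that the measurement the trial hopes to promote is post-PCI FFR. This also stands. A patient who reaches that measurement has already had PCI and is in the Safety Set on either reading.

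**Conclusion.** The point holds in a limited form, and its severity is minor. Read plainly, the Safety Set leaves out a patient stopped during the pre-PCI study tests, and with that patient any SAE that caused the stop. The SAE summary loses the event. So does the fatal-SAE summary, by inference from its place in 2.5.3, since that sentence names no set.

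The conclusion rests on treatment meaning the PCI strategy and not the tests. It does not depend on whether randomisation or testing comes first.

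The number affected is unknown and probably small. The rates in the working are assumptions, and nothing in the documents favours one of them.

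Two stronger readings should be resisted. The arm comparison is not materially biased: under the protocol the arms diverge only after the first post-PCI FFR, so losses before PCI fall on both arms alike in expectation. Nor does the gap cast doubt on the reported safety of post-PCI FFR or of the optimisation steps, which come after PCI.

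**What to change.** In SAP 2.1, define the safety population as all patients in whom any study procedure was started (pressure wire introduced for the study tests, or study adenosine given), whether or not PCI or optimisation followed. Name this population in 2.5.2, in 2.5.3 and for the fatal-SAE summary. Show patients stopped before PCI on a separate line. If the pre-PCI tests come before randomisation, include on that line consented patients in whom the tests were started but who were not yet randomised.

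The cost is a revised definition and the cross-references to it. No new data collection is evident, since adverse events of the tests are already to be collected. The downside is that the reported SAE rate may be slightly less favourable.

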2.2 Baseline Characteristics

Baseline characteristics will be summarised in the FAS as a whole and by treatment group. The following baseline characteristics will be reported:

- Demographics: age (years), sex (male, female), height, weight, BMI, ethnicity (White or White British, Asian or Asian British: South Asian, Asian or Asian British: Chinese, Asian or Asian British: Other Asian, Black or Black British, Mixed or Multiple, Other)
- Lifestyle Factors: Smoking Status (No, Current, Ex-Smoker <12 months, Ex-Smoker >12 months)
- Vital Sign Observations: heart rate, blood pressure
- Pharmaceutical therapy (medications used for treatment of cardiovascular disorders including primary and secondary therapies)
 - Number of antianginal medications
- Medical History including Risk Factors (yes/no unless otherwise stated)
 - Indication for Angiogram (Stable Angina, ACS-NSTEMI, ACS-Unstable Angina)
 - Time since NSTEMI
 - Troponin Assay Used and Peak Troponin Recorded if NSTEMI
 - Hypertension
 - Hypercholesterolaemia
 - Diabetes
 - TIA/Stroke
 - CKD
 - Thyroid Dysfunction
 - Pacemaker
 - ICD
 - Atrial Fibrillation
 - Heart Failure (No, HF-rEF, HF-pEF)
 - NYHA Class if Heart Failure (1-4)
 - Previous PCI
 - Previous MI
 - History of Previous MI in Target Vessel if Yes
 - CABG
 - Angina
 - Canadian Cardiovascular Society (CCS) Class if Angina (1-4)
 - Valvular Heart Disease
 - Valve Replacement/Repair
 - Family History of CAD
- Health Status questionnaire scores:
 - Seattle Angina Questionnaire
 - EQ-5D-5L
- Procedural Characteristics
 - Vascular Access (Radial, Femoral, Brachial)
 - Sheath Size

- Multivessel Procedure (Yes, No)
- Procedure Time
- Duration of Research Protocol
- Contrast Dose
- Dose Area Product
- Radiation Dose
- Total Duration of Adenosine Infusion
- Total Dose of Adenosine
- Total Number of Stents Deployed in Study Artery
- Total Length of Stents Used in Study Artery
- Diameter of Largest Balloon used for PCI
- Largest Stent Diameter

- Angiographic Characteristics
 - Target Coronary Artery Segment
 - Lesion Severity by Operator's Visual Assessment (Normal, Plaque Disease, <25%, 25-49%, 50-74%, 75-94%, >/= 95%, Subtotal Occlusion, Occluded)
 - AHA Lesion Type
 - Lesion APPROACH Score
 - Gensini Score
 - QCA Lesion Length
 - Pre- and Post-PCI QCA Diameter Stenosis
 - Pre- and Post-PCI QCA Area Stenosis
- Pre- and Post-PCI Coronary Physiology Test Results
 - Ratio of distal coronary to aortic pressure (Pd/Pa)
 - Diastolic Pressure Ratio (dPR)
 - Resting Full-cycle Ratio (RFR)
 - Mean Resting Transit Time
 - Fractional Flow Reserve (FFR)
 - Mean Hyperaemic Transit Time
 - Coronary Flow Reserve (CFR)
 - Index of Microcirculatory Resistance (IMR)
 - IMR corrected by Yong's Formula (IMRc)
 - Presence of 'Abrupt Drop' pattern on pressurewire pullback assessment
 - Time to Hyperaemia
 - Presence of Pressure Wire Drift >/=0.04 on pullback
 - Requirement for Repeat Assessment due to Drift
 - Chest Discomfort During Adenosine Infusion (None, Slight, Moderate, Severe)
 - Pre-PCI 'Grey Zone' FFR (0.75-0.80) Value (Yes/No)
 - Final FFR ≥0.90 (Yes/No)
 - Final FFR ≥0.80 (Yes/No)

